### 3.2.5. OS

OS is measured from the date of first dose until the occurrence of death due to any cause, censored at the last known alive date for those without events.

### 3.2.6. PK Endpoints

PK profiles of bosutinib will be determined using a sparse sampling regimen and population PK analysis approach. A total of 4 PK samples per patient will be drawn. All patients will provide pre-dose blood samples on Day 1, Day 28, Day 56, and Day 84.

PK endpoints and analyses include:

- Population PK of bosutinib, and
- Correlations between trough concentrations of bosutinib and key efficacy and safety endpoints.

### 3.3. Other Endpoints

The following endpoints will be assessed exploratorily:

- MMR at 3, 6, 9 and 18 months;
- MMR at 12 months in patients with both Ph+ and Ph- CP CML;
- MR^1 and MR^2 at 3 and 6 months, respectively;
- MR4.0 and MR4.5 at 3, 6, 9 and 12 months;
- Time to MMR, MR4.0, MR4.5 and CCyR;
- Cumulative CHR in patients with Ph+ and both Ph+ and Ph- CP CML;
- Time to transformation to AP and BP CML on treatment;
- Type of mutations present at treatment completion/discontinuation or suboptimal response;
- Potential results from exploratory analyses of banked biospecimen (these results may or may not be generated in the context of the present study).

### 3.4. Baseline Variables

The baseline will be defined as the last non-missing assessment prior to the first dose of study drug. An assessment on Day 1 is assumed to be pre-dose of study drug unless otherwise specified.

The following variables will be collected only during screening period:

- Demographics (gender, age and race);
- Sokal score;
- Medical and cancer history;
- Blood chemistry (hepatitis B virus (HBV) and hepatitis C virus (HCV) test);
- Height.

The age will be calculated as the number of elapsed years from date of birth to date of screening.

The Sokal score is derived by study sites using the following formula:

$$\exp(0.0116(\text{Age} - 43.4) + 0.0345(\text{Spleen} - 7.51) + 0.188((\text{Platelet} / 700)^2 - 0.563) + 0.0887(\text{Blasts} - 2.1)),$$

where units of Age, Spleen, Platelet and Blasts are years, centimeters below costal margin,  $10^9/\text{L}$  and percentage of blasts in peripheral blood, respectively.

There are no stratification factors nor covariates in this study.

### 3.5. Safety Endpoints

Safety endpoints are the secondary endpoints in this study.

#### 3.5.1. Adverse Events

An adverse event (AE) is any untoward medical occurrence in a study patient administered a product or medical device; the event need not necessarily have a causal relationship with the treatment or usage.

A treatment-emergent adverse event (TEAE) is defined as an AE that first occurred or worsened in severity from the first dose of the study drug until 28 days after the last dose. TEAEs will be assessed mainly in this study.

#### 3.5.2. Laboratory Data

The following laboratory parameters will be assessed:

- Complete blood count (CBC) including WBC count with 5-part differential, absolute neutrophil count (ANC), platelet count, red blood cell (RBC) count and hemoglobin;
- Liver function measurements† including aspartate aminotransferase (AST), alanine aminotransferase (ALT), total bilirubin;
- Blood chemistry including sodium, potassium, chloride, carbon dioxide or bicarbonate (if available), blood urea nitrogen (BUN) or urea, creatinine, glucose, total protein, albumin, calcium, alkaline phosphatase, amylase, lipase, phosphorous, magnesium, creatine kinase and uric acid (until patient achieves CHR);
- Coagulation test including prothrombin time (PT) or international normalized ratio (INR) and partial thromboplastin time (PTT) or activated partial thromboplastin time (aPTT);
- Urinalysis including urine protein and urine blood, and
- Estimated glomerular filtration rate (eGFR) calculated by study sites using the following Modification of Diet in Renal Disease (MDRD) formula;

$$32788 \times (\text{Creatinine} / 88.4) - 1.154 \times \text{Age} - 0.203 \times 0.742 (\text{if female}) \times 1.21 (\text{if black}).$$

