4.1. Inclusion Criteria

Patients must meet all of the following inclusion criteria to be eligible for enrollment into the study:

1. Diagnosis of CP CML of ≤ 6 months (from initial diagnosis)
 - Diagnosis of CP CML with molecular confirmation by detection of BCR-ABL rearrangement at screening (cytogenetic assessment for Ph is not required for enrollment; however, patients with known Ph- CML prior to registration are not eligible for this study); diagnosis of CP CML will be defined as all of the following per European LeukemiaNet (ELN) definitions:

- a. <15% blasts in peripheral blood and bone marrow;
 - b. <30% blasts plus promyelocytes in peripheral blood and bone marrow;
 - c. <20% basophils in peripheral blood;
 - d. $\geq 100 \times 10^9/L$ platelets ($\geq 100,000/mm^3$);
 - e. No evidence of extramedullary disease except hepatosplenomegaly; AND
 - f. No prior diagnosis of AP or BP-CML.
2. Age ≥ 20 years.
 3. Eastern Cooperative Oncology Group (ECOG) performance status (PS) 0 or 1.
 4. Adequate Renal Function, including:
 - a. Serum creatinine $\leq 1.5 \times$ upper limit of normal (ULN) or estimated creatinine clearance ≥ 60 mL/min as calculated using the method standard for the institution.
 5. Adequate Liver Function, including:
 - a. Total serum bilirubin $\leq 1.5 \times$ ULN unless the patient has documented Gilbert syndrome;
 - b. AST and ALT $\leq 2.5 \times$ ULN; $\leq 5.0 \times$ ULN if there is liver involvement by leukemia;
 6. Able to take oral tablets.
 7. Resolved acute effects of any prior therapy to baseline severity or CTCAE Grade ≤ 1 except for AEs not constituting a safety risk by investigator judgment.
 8. Serum pregnancy test (for females of childbearing potential) negative at screening.

Female patients of nonchildbearing potential must meet at least 1 of the following criteria:

- a. Achieved postmenopausal status, defined as follows: cessation of regular menses for at least 12 consecutive months with no alternative pathological or physiological cause; status may be confirmed with a serum follicle-stimulating hormone (FSH) level confirming the postmenopausal state;
- b. Have undergone a documented hysterectomy and/or bilateral oophorectomy;
- c. Have medically confirmed ovarian failure.

All other female patients (including female patients with tubal ligations) are considered to be of childbearing potential.

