### **6.6.2. Laboratory Data**

Laboratory results including bone marrow aspirate will be classified according to the NCI CTCAE version 4.03. Laboratory results that are not part of NCI CTCAE or are impossible to be classified according to the NCI CTCAE using laboratory data only will be presented according to the categories: below normal limit, within normal limits and above normal limit (according to the laboratory normal ranges). Kidney Disease Improving Global Outcomes (KDIGO) categories (see [Appendix 1.5](#)) will be used for eGFR grading.

Laboratory assessments will be presented as mean changes from baseline and incidence of abnormal values. Shift tables will also be presented.

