#### Appendix 1.5. KDIGO Categories

eGFR Category	eGFR (ml/min/1.73 m  )	Terms
1	$\geq 90$	Normal or high
2	60–89	Mildly decreased
3a	45–59	Mildly to moderately decreased
3b	30–44	Moderately to severely decreased
4	15–29	Severely decreased
5	$<15$	Kidney failure

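### The eGFR formula printed in SAP 3.5.2 applies the creatinine unit conversion twice, so values computed from it would all fall in KDIGO category 1

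*SAP*

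**What the plan says.** SAP 3.5.2 (Laboratory Data) includes among the laboratory parameters "Estimated glomerular filtration rate (eGFR) calculated by study sites using the following Modification of Diet in Renal Disease (MDRD) formula". The formula has the constant 32788, creatinine divided by 88.4, the coefficients 1.154 and 0.203 for creatinine and age, and factors of 0.742 for women and 1.21 for black patients. It gives no unit for creatinine.

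SAP 6.6.2 says that KDIGO categories "will be used for eGFR grading". It also plans mean changes from baseline, counts of abnormal values and shift tables for laboratory data. SAP Appendix 1.5 sets the scale in ml/min/1.73 m²: category 1, labelled "Normal or high", is 90 or more, and category 5 is below 15.

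The protocol schedules eGFR in the Schedule of Activities. The notes to its Table 4 say only that eGFR will be calculated. It gives no formula that would replace or correct the one in the SAP.

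**The concern.** The constant and the divisor look like alternatives. Dividing by 88.4 takes creatinine from µmol/L to mg/dL, and a constant as large as 32788 is what one would expect if that conversion had already been absorbed. If both are used, the result is far off the scale on which the SAP grades it.

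What is at stake is one planned safety output. The KDIGO categories and their shift table are meant to show movement from better to worse kidney function on treatment. If every value lies above 90, no movement can appear.

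**Working it through.** **Inputs.** The constant 32788, the divisor 88.4, the coefficients −1.154 and −0.203 and the sex factor 0.742 are from SAP 3.5.2. The category limits are from SAP Appendix 1.5. The race factor is set to 1, since the patients are Japanese.

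**Assumptions.** The two coefficients are read as exponents, since superscripts are lost in the text as extracted; that loss is not counted as an error. Creatinine (Cr) is taken in µmol/L, because 88.4 is the divisor from µmol/L to mg/dL. The plan states no eGFR value that could be reproduced first.

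**Step 1: is the conversion already in the constant?**
- As printed: E1 = 32788 × (Cr/88.4)^−1.154 × Age^−0.203 × 0.742 (women)
- One conversion: E2 = 32788 × Cr^−1.154 × Age^−0.203 × 0.742 (women)
- Ratio: E1/E2 = 88.4^1.154 = 176.28, the same for every creatinine, age and sex
- Equivalent constant with the divisor kept: 32788/176.28 = 186.0

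**Step 2: one case in full.** For a man aged 50 with Cr = 88.4, the creatinine term in E1 is 1 and 50^−0.203 = 0.452. So E1 = 32788 × 0.452 = 14,819 (unrounded factor), and E2 = 14,819/176.28 = 84.1.

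**Step 3: a range of cases.**

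| Patient | Cr (µmol/L) | As printed | KDIGO | One conversion | KDIGO |
|---|---|---|---|---|---|
| Man, 50 | 88.4 | 14,819 | 1 | 84.1 | 2 |
| Man, 50 | 132.6 | 9,281 | 1 | 52.7 | 3a |
| Woman, 80 | 132.6 | 6,260 | 1 | 35.5 | 3b |
| Man, 50 | 200 | 5,776 | 1 | 32.8 | 3b |
| Man, 50 | 400 | 2,596 | 1 | 14.7 | 5 |

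Over creatinine 50 to 800 µmol/L, ages 20, 50 and 80 and both sexes, the printed formula gives 787 to 34,451, always category 1. With one conversion the same grid gives 4.5 to 195.4, and all six categories occur.

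**Step 4: what would it take to leave category 1?** Setting E1 = 90 for a man aged 50 gives Cr = 88.4 × (14,819/90)^(1/1.154) = 88.4 × 83.3, or about 7,400 µmol/L. Put another way, the single-conversion eGFR would have to fall below 90/176.28 = 0.51.

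**Step 5: does another reading rescue the formula?**
- Creatinine entered in mg/dL: a man aged 50 at 1.0 mg/dL gets about 2.6 million.
- No exponents, read as a plain linear expression: a man aged 50 at 88.4 gets 32788 − 1.154 × 50 − 0.203 = 32,730, and the value rises with creatinine.

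Neither gives a value that the KDIGO table can grade.

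**Step 6: what would still be visible?** If creatinine rises from 88.4 to 132.6 in the man aged 50, eGFR is multiplied by 1.5^−1.154 = 0.626 under either formula. As printed, the change is 9,281 − 14,819 = −5,538, with category 1 before and after. With one conversion it is 52.7 − 84.1 = −31.4, a shift from category 2 to 3a. The relative fall is the same; only the category change is lost.

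**The case against.** The strongest reply is that the analysis takes in a value supplied by the sites, and nothing shows that any site used the printed line. The SAP is an analysis document kept by the sponsor. The protocol, which sites work from, gives no eGFR formula, and for creatinine clearance at eligibility it accepts a value "as calculated using the method standard for the institution". The SAP describes other site-derived values in the same way, such as the Sokal score in 3.4 and QTcF in 3.5.4. The eGFR line may therefore be a transcription error in a description of method. This stands: a reader might infer that all patients will be misgraded, or that sites have been told to use this formula, and the documents establish neither.

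A reader might also infer that a decline in renal function would go unseen. That does not follow even if the formula is used. Creatinine is a laboratory parameter in its own right (SAP 3.5.2) and is summarised under SAP 6.6.2. The renal adverse event category in SAP Appendix 2 includes raised creatinine, reduced clearance or filtration rate, and renal failure and impairment. A proportional fall in eGFR would still show in the mean change from baseline, though on a scale 176 times too large.

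Finally, values in the thousands would probably be noticed on first review. That makes silent misgrading less likely. It does not correct the text, and it gives no rule for what to do once the values are noticed.

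**Conclusion.** The printed formula is wrong as written, and the SAP's own KDIGO table is enough to show it, without recourse to any published equation. Computed as printed, eGFR is too high by a factor of 176.

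The exact factor rests on reading the coefficients as exponents and creatinine as µmol/L. The conclusion that every value falls in category 1 holds under the other readings checked.

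The consequence is conditional. If sites follow the printed line, the KDIGO grading and shift table are uninformative. If they use something else, the SAP reports a method that was not applied. Either way the text needs correcting.

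The reach is limited to that output. The primary test of MMR at 12 months does not use eGFR, and eligibility rests on serum creatinine or creatinine clearance. This is a correction that should be made before the safety tables are produced, not a threat to the trial's main conclusion.

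**What to change.** In SAP 3.5.2, state the unit of creatinine and keep one conversion only. Either use 32788 with creatinine in µmol/L and no division, or use 186 with creatinine in µmol/L divided by 88.4. SAP 3.5.4 already follows the practice of stating the unit when it derives heart rate from the RR interval.

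Then confirm that the site-reported eGFR values used for KDIGO grading follow the corrected formula. If they do not, or if this cannot be confirmed, derive eGFR in the analysis dataset from creatinine, age and sex. Central derivation is not needed if the site values are confirmed.

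The cost is one line of SAP text and one query to the sites. At most it adds one derived variable, and all of its inputs are already collected.

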### 3.5.3. Vital Signs and Body Weight

Temperature (axillary), supine blood pressure, heart rate and body weight will be assessed.

### 3.5.4. Electrocardiograms

Triplicate 12-lead (with a 10 second rhythm strip) tracings will be used for all electrocardiograms (ECGs). A QT interval will be corrected for an RR interval using Fridericia's (QTcF) and Bazett's factors (QTcB), respectively. Actually, QTcF will be reported by study sites. On the other hand, QTcB will be derived from  $QT / RR^{1/2}$ . A heart rate will be derived from  $60000 / RR$  if the unit of RR is msec.

At each time point, 3 consecutive ECGs will be performed at approximately 2 minutes apart to determine the mean QTcF and QTcB intervals.

### 3.5.5. Echocardiogram or Multiple Gated Acquisition

Echocardiogram (ECHO) or multiple gated acquisition (MUGA) will be performed at screening (within 2 weeks prior to registration) and at End of Treatment/Withdrawal or at Week 96, whichever is earlier, and as clinically indicated.

---

† Direct and indirect bilirubin are specified in the study protocol to evaluate the liver function as needed. However, the result of measurement will not be collected in the CRF. Therefore, they are removed from the SAP.

#### **4. ANALYSIS SETS**

Data for all patients will be assessed to determine if patients meet the criteria for inclusion in each analysis population prior to releasing the database and classifications will be documented per standard operating procedures.

##### **4.1. As-Treated Population**

The as-treated population will consist of all enrolled patients who received at least 1 dose of study drug. Since this is a single-arm phase 2 study, as-treated population is also the full analysis set.

##### **4.2. Modified as-Treated Population**

The modified as-treated population will consist of all enrolled patients with Ph+ CP CML harboring b2a2 and/or b3a2 transcripts who received at least 1 dose of study drug.

##### **4.3. Safety Analysis Set**

The safety population will consist of all enrolled patients, regardless of Ph status, who received at least 1 dose of study drug. This means that the as-treated population is also the safety analysis set. Therefore, the as-treated population will be presented in any tables, listings and figures instead of the safety analysis set.

##### **4.4. PK Analysis Set**

The PK population will be defined as any patient in the safety population of patients who had at least 1 concentration of bosutinib on-treatment.

## **5. GENERAL METHODOLOGY AND CONVENTIONS**

### **5.1. Hypotheses and Decision Rules**

In this study, null ( $H_0$ ) and alternative ( $H_1$ ) hypotheses are as follows:

$H_0$ : the true MMR rate at 12 months (48 weeks) is 25%;

$H_1$ : the true MMR rate at 12 months (48 weeks) is 40%.

With 60 Ph+ patients, the study is powered at greater than 82% to test this null versus alternative hypothesis with one-sided alpha of 5%. The MMR rate at 12 months will be considered >25% if and only if the null hypothesis is rejected (observing at least 21 responders [35%] out of the 60 total patients). The statistical comparison will be performed after Core Treatment Phase of all treated patients. No multiplicity adjustment will be needed.

No formal statistical hypothesis tests will be performed for any endpoints except for the primary endpoint.

### **5.2. General Methods**

#### **5.2.1. Analyses for Continuous Data**

Continuous data will be summarized descriptively (n, mean, standard deviation, minimum, median, maximum) unless otherwise specified.

#### **5.2.2. Analyses for Categorical Data**

Categorical data will be summarized using the frequency table (the number of patients, frequency and percentage). An asymptotic confidence interval (CI) of estimated proportion for response rate will also be presented as needed.

#### **5.2.3. Analyses for Time-to-Event Data**

Time-to-event data (duration of response and OS) will be summarized using the Kaplan-Meier method and estimated survival curves will be displayed graphically when appropriate. Graphs will describe the number of patients at risk over time. The median, quartiles and probabilities of an event at particular points in time will be estimated by the Kaplan-Meier method. CIs for medians and quartiles are based on the Brookmeyer-Crowley method. CIs for the estimated probability of event at a particular time point will be generated using the Greenwood's formula. When applying the cumulative incidence method (time to response and transformation, EFS), yearly rates with the associated CI based on delta method with log(-log) transformation method will be provided. Percentiles of the cumulative incidence function (25%, 50% and 75%) will also be provided.

### **5.3. Methods to Manage Missing Data**

#### **5.3.1. Molecular Response Assessment**

##### **5.3.1.1. MMR, MR4.0 and MR4.5 at 12 months (48 weeks)**

If a patient is missing a molecular response assessment at 48-week visit, and patient demonstrates response at both the 36-week and 60-week visits, then that patient will be considered a responder at the 48-week visit. In other situation, a patient will be considered a non-responder at the 48-week visit.

##### **5.3.1.2. MMR at 18 months (72 weeks)**

The same rules apply for MMR at 18 months as they do for MMR at 12 months. In this case, the 60-week and 84-week visits will be used for a missing molecular assessment.

##### **5.3.1.3. MR^1 and MR^2 at 3 and 6 months**

If a patient is missing the assessment, they will be coded as a non-responder.

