- s. RT-qPCR testing for BCR-ABL will be performed at Screening, at 12, 24, 36, and 48 weeks during the Core Treatment Phase and then every 12 weeks until the end of Year 2, then every 24 weeks. If a ≥ 5 -fold increase in BCR-ABL transcripts from the lowest value achieved on study along with loss of MMR is identified and confirmed by duplicate analysis of the same sample, an unscheduled visit sample will be collected within 4-6 weeks to confirm the results. Fifteen (15) mL peripheral blood will be collected at each designated time-point. Additional 5 mL blood will be collected at Week 48; these will serve as back-up samples for the primary endpoint. For patients who achieve undetectable BCR-ABL by RT-qPCR, 20 mL of blood may be collected for PCR analysis. In addition, after the first documented negative BCR-ABL result, 20 mL of blood will be collected for all subsequent sampling time-points until BCR-ABL is no longer negative. 20 mL of blood may be collected as an unscheduled PCR sample from these patients.
- t. Mutation analysis will be performed in case of either lack of response, suboptimal response or loss of response defined as: failure to achieve MMR at 12 months; loss of MMR AND rise in BCR-ABL transcript level by ≥ 5 -fold from the lowest value achieved during the study; at the End of Treatment/Withdrawal visit. No mutation analysis will occur at screening. For patients with a positive mutation identified during therapy, follow-up

mutation analyses will be performed in subsequent samples. For a patient with a negative mutation result immediately following relapse, continued mutation analyses may be performed at a frequency of every 6 months (every 24 weeks) as needed.

- u. AEs should be documented and recorded at each visit using the NCI CTCAE version 4.03. The time period for actively eliciting and collecting AEs and SAEs (“active collection period”) for each patient begins from the time the patient provides informed consent through and including a minimum of 28 calendar days after the last investigational product administration. If a patient begins a new anticancer therapy, the period for recording non-serious AEs on the CRF ends at the time the new treatment is started. However, any SAEs occurring during the active collection period must still be reported to Pfizer Safety and recorded on the CRF, irrespective of any intervening treatment.

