##### **5.3.1.5. MMR, MR4.0 and MR4.5 at 6 and 9 months**

If a patient is missing a molecular response assessment at the time of interest and the patient demonstrates molecular response at both prior and subsequent visits, then that patient will be considered a responder at that time of interest. If a patient is missing molecular response at either prior or subsequent visits, then that patient will be considered a non-responder at that time of interest.

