#### **6.3.2. Molecular Response**

Measures of MR^1, MR^2, MR4.0 and MR4.5 at each pre-specified visit will be evaluated by frequency tables. The two-sided 90% CI will also be calculated.

Pre-specified visits for MR^1 and MR^2 are 3 and 6 months, respectively, while pre-specified visits for MR4.0 and MR4.5 are 3, 6, 9 and 12 months.

These analyses will be performed using the modified as-treated population and the as-treated population, respectively.

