## 9. APPENDICES

### Appendix 1. Response Definitions

#### Appendix 1.1. Molecular Responses

Before Treatment	Molecular Response	RT-PCR (BCR-ABL Ratio)
Chronic Phase	Major, or MMR	≤0.1% (corresponding to ≥3 log reduction from baseline a ) with a minimum number of ABL transcripts specified by the central laboratory
	MR 	A 1 log reduction in BCR-ABL transcript with a minimum number of ABL transcripts specified by the central laboratory
	MR 	A 2 log reduction in BCR-ABL transcript with a minimum number of ABL transcripts specified by the central laboratory
	MR 4.0	Either (i) detectable disease with ≤0.01% BCR-ABL IS or (ii) undetectable disease in cDNA with a minimum number of ABL transcripts specified by the central laboratory
	MR 4.5	Either (i) detectable disease with ≤0.0032% BCR-ABL IS or (ii) undetectable disease in cDNA with a minimum number of ABL transcripts specified by the central laboratory in the same volume of cDNA used to test for BCR-ABL

a. Standardized baseline from central laboratory.

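### A missing Week 24 sample is scored by two unharmonised rules at 6 months, so a patient can count as an MMR responder and an MR2 non-responder

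*SAP*

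**What the plan says.** MR1 and MR2 are each analysed at one visit. SAP 6.3.2 states: "Pre-specified visits for MR 1 and MR 2 are 3 and 6 months, respectively". For both, SAP 5.3.1.3 has a single missing-data rule: "If a patient is missing the assessment, they will be coded as a non-responder".

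For MMR, MR4.0 and MR4.5 at 6 and 9 months, SAP 5.3.1.5 applies when the sample is absent but "the patient demonstrates molecular response at both prior and subsequent visits, then that patient will be considered a responder at that time of interest". If either neighbouring assessment is also missing, the patient is a non-responder.

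SAP Appendix 1.1 defines MMR as "≤0.1% (corresponding to ≥3 log reduction from baseline", with a footnote tying that baseline to the central laboratory's standardized value. It defines MR2 as "A 2 log reduction in BCR-ABL transcript with a minimum number of ABL transcripts specified by the central laboratory".

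The samples needed on either side of Week 24 are already scheduled. Footnote s of the protocol's Schedule of Activities says: "RT-qPCR testing for BCR-ABL will be performed at Screening, at 12, 24, 36, and 48 weeks during the Core Treatment Phase".

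MR2 at 6 months falls under SAP 3.3, which opens: "The following endpoints will be assessed exploratorily".

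**The concern.** One absent blood sample feeds four 6-month endpoints. Three of them can be rescued by the visits before and after; the shallowest cannot. Because a patient in MMR should also be in MR2, the two rules can place one patient in the deeper category and outside the shallower one.

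The strict rule is understandable at 3 months, where there is no earlier on-treatment PCR visit. There it applies equally to MR1 (SAP 5.3.1.3) and to MMR, MR4.0 and MR4.5 (SAP 5.3.1.4), so no conflict arises. At 6 months MR2 has a scheduled sample on each side and is the only molecular endpoint denied their use.

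Elsewhere the SAP lets a deeper response supply a shallower one. SAP 5.3.2 imputes CCyR from MMR when cytogenetics are unavailable. SAP 5.3.3 imputes CHR from MMR or CCyR when components are missing and those assessed are within limits. The treatment of MR2 goes against that practice.

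At stake is whether the 6-month MR2 rate can be compared with the 6-month MMR, MR4.0 and MR4.5 rates, and whether the patient-level classification is coherent.

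**Working it through.** **The plan's own figure.** The documents give no expected rate for MR2. The only design figure is the power of the primary test, and this point does not depend on it. It reproduces: with n = 60, rates of 25% and 40% and one-sided 5%, power = Φ[(0.15 − 1.645 × √(0.25 × 0.75/60)) / √(0.40 × 0.60/60)] = Φ(0.918) = 82.07%, against the stated 82.1% (protocol 9.1).

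**Thresholds.** If 0.1% corresponds to 3 log, the standardized baseline is 100%, since 100% × 10⁻³ = 0.1%. Two log from the same baseline is 100% × 10⁻² = 1%. The other entries in SAP Appendix 1.1 fit this scale: 100% × 10⁻⁴ = 0.01% (MR4.0) and 100% × 10⁻⁴·⁵ = 0.0032% (MR4.5).

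**The two rules applied to one patient with no Week 24 sample** (illustrative values):

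| Week 12 | Week 36 | MMR at 6 months (5.3.1.5) | MR4.0 at 6 months (5.3.1.5) | MR2 at 6 months (5.3.1.3) | MR2 if 5.3.1.5 applied |
|---|---|---|---|---|---|
| 0.08% | 0.03% | responder | non-responder | non-responder | responder |
| 0.009% | 0.002% | responder | responder | non-responder | responder |
| 0.5% | 0.05% | non-responder | non-responder | non-responder | responder |

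The first two rows are the contradiction. The third shows that the loss extends to patients with MR2 but not MMR at both neighbouring visits, where nothing looks wrong.

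**Direction.** A change from 5.3.1.3 to 5.3.1.5 can only turn MR2 non-responders into responders. Relative to the rule for the other endpoints, the current MR2 rate is therefore lower or equal, never higher.

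**Size.** Let k be the number of patients with a missing Week 24 sample and MR2 shown at both Week 12 and Week 36. The difference is k/60:
- k = 0: 0 points
- k = 1: 1.67 points
- k = 2: 3.33 points
- k = 3: 5.00 points

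The documents give neither a missing-sample rate nor an expected MR2 rate, so k cannot be estimated from them.

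**Who is not affected.** A patient who stops before Week 24 and has no Week 36 sample is a non-responder under both rules. Only isolated gaps count towards k.

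**The case against.** **Conservative and prespecified.** Scoring missing as non-response is a standard convention, fixed in advance and used for other endpoints in this SAP. That would be sufficient if it covered every response depth at the visit. Applied to the shallowest alone, it breaks the ordering of the endpoints.

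**MR2 is analysed at one visit only.** MMR, MR4.0 and MR4.5 are derived at several visits, so their neighbouring values are planned derivations; MR2 at Weeks 12 and 36 is not. The SAP does not give this as its reason, but the difference is real. It does not prevent the fix, because the PCR values are collected at those weeks anyway.

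**The definition of MR2 is loose.** SAP Appendix 1.1 does not say from which baseline the 2-log fall is measured, or that it means at least 2 log. A reader might infer that MMR without MR2 is impossible by definition; the text does not go that far. If MR2 were measured from the patient's own screening value, MMR could occur without it. This would need a screening value below 100 × 0.1% = 10%, because from 10% upwards a level of 0.1% is already a 2-log fall. The common-baseline reading fits the rest of the table better, but it is an assumption.

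**Little depends on it.** SAP 5.1 tests only the primary endpoint. MR2 at 6 months is in neither the interim-look list (SAP 7.2.1.2) nor the final-analysis list (SAP 7.2.3). Individual data will be listed (protocol 9.2), so an affected patient could be found. For scale, at an assumed rate of 60% the half-width of the 90% interval is 1.645 × √(0.6 × 0.4/60) = 10.4 points. All of this stands, and it makes the point minor.

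**Conclusion.** The point holds as a minor inconsistency. Two stated rules give incoherent results for the same missing sample, and nothing in either document resolves them. It rests on reading MR2 as at least a 2-log fall from the standardized baseline used for MMR. The size is 1.67 points per affected patient at N = 60, always downward relative to the 5.3.1.5 rule, with an unknown total that may be zero.

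A reader might infer a material understatement of the MR2 rate. For example, if 3 to 10% of Week 24 samples were missing and 60% of those patients had MR2 at both neighbouring visits, 1.1 to 3.6 of 60 responders would be lost, or 1.8 to 6 points. The documents support neither input. The sum also treats every missing sample as an isolated gap, although patients who have left by Week 36 score the same under both rules. The visible contradiction is narrower still, since it needs MMR already at Week 12.

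Nor should a reader infer any effect on the trial's conclusion. The primary endpoint at 48 weeks has its own missing-data rule (SAP 5.3.1.1), and its test and power are unchanged.

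**What to change.** Move MR2 at 6 months from SAP 5.3.1.3 to the rule of 5.3.1.5: a missing Week 24 sample counts as MR2 if MR2 is shown at both Week 12 and Week 36, and as non-response otherwise. Leave MR1 at 3 months unchanged. The explicit fallback also settles the case where a neighbouring visit is observed without response, which 5.3.1.5 does not spell out.

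In the same edit, state in Appendix 1.1 that MR2 is a fall of at least 2 log from the standardized baseline, if that is what is meant.

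A rule that a deeper response implies the shallower one would remove the visible contradiction, but it would leave patients with only MR2 at both neighbouring visits under the stricter rule. Moving the endpoint deals with both.

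The cost is a line or two of SAP text and the derivation of MR2 at Weeks 12 and 36 from samples already scheduled. It needs no new visits, data or patients. It should be settled before the analysis, so that the choice is not made with the data in view.
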